**Table 21      Laboratory Parameters for Descriptive Statistics and Shift Table**

Lab Panel	Analysis Time Point	Parameter
Hematology and Coagulation	Baseline	Hemoglobin Hematocrit
	Treatment period	Erythrocytes (Red blood cell [RBC]) Leukocytes (White blood cell [WBC]) Differential WBC
	Week 2, Week 4, Week 8,	Platelets PT and INR
	Follow-up	MCV MCH
	Week 10	Reticulocytes
Biochemistry	Baseline	Sodium Potassium
	Treatment period	Calcium Chloride
	Week 2, Week 4, Week 8,	Magnesium Glucose
	Follow-up	Creatine Kinase Creatinine
	Week 10	Alkaline Phosphatase (ALP) Lactate dehydrogenase (LDH) Aspartate transaminase (AST) Alanine transaminase (ALT) Gamma glutamyl transpeptidase (GGT) Total bilirubin (direct and indirect) Total protein Albumin Total cholesterol Triglycerides Uric Acid Blood Urea Nitrogen (BUN) Inorganic phosphate

All laboratory measurements, including the derived outcomes (change from baseline and flagging of abnormal value with high and low) will be presented in the listing. Urinalysis will be listed only.

#### **7.5.3.1 Liver Enzymes and Total Bilirubin**

The following potentially clinically significant (PCS) criteria for liver tests – defined as Alkaline Phosphatase (ALP), Alanine Transaminase (ALT), total bilirubin (TBL), Aspartate Transaminase (AST), International Normalized Ratio (INR) and their combination are defined.

**Table 22 Potentially Clinically Significant Criteria for Liver Enzymes and Total Bilirubin**

Parameter	Criteria
ALT	> 3xULN > 5xULN > 10xULN > 20xULN
AST	> 3xULN > 5xULN > 10xULN > 20xULN
ALT or AST	> 3xULN
TBL	> 2xULN
INR	> 1.5 (Ratio)
ALP	> 1.5xULN
ALT and/or AST AND TBL (*)	(ALT and/or AST > 3xULN) and TBL > 2xULN
ALT and/or AST AND TBL and/or INR(*)	(ALT and/or AST > 3xULN) and (TBL > 2xULN and/or INR > 1.5

(\*) Combination of values measured from the samples collected on the same day.

The number and percentage of subjects with PCS values in liver enzyme and total bilirubin tests using the subject's highest value during the double-blind treatment period will be presented by treatment group. Another summary will be created using the subject's highest value during the follow-up period.

In addition to the above summaries the following data will be presented graphically by treatment group:

- Scatter plot of maximum values for ALT or AST and TBL during the double-blind treatment period and follow-up period with ALT or AST values on x-axis and TBL values on y-axis [Senior, 2014], and
- Individual display of liver enzymes and TBL for selected subjects experiencing potentially clinically significant criteria of ALT > 3xULN or AST > 3xULN or TBL > 2xULN during double-blind treatment period or follow-up period.

### 7.5.3.2 Potentially Clinically Significant Laboratory Criteria

Potentially clinically significant laboratory criteria for other laboratory variables are provided in Section 10.3 Appendix 3: Potentially Clinically Significant Laboratory Criteria. The number and percentage of subjects with PCS values using the subject's highest and/or lowest value (depending on the direction of interest) during the double-blind treatment period will be presented by treatment group. Another summary will be created using the subject's highest and/or lowest value (depending on the direction of interest) during the follow-up period.

### 7.5.4 Vital Signs

The baseline visit is the last measurement taken prior to the first dose of study drug.

Supine (average)/resting vital signs (SBP, DBP and pulse rate) will be summarized using mean, SD, minimum, maximum and median by treatment group and visit (Baseline, Day 1 2-hours post-dose, Week 2, Week 4, Week 8/EOT, Week 10). Additionally, a within-subject change will be calculated per visit as the post-baseline measurement minus the baseline measurement and summarized by treatment group and visit. Section 7.11.5.3 describes the derivation of visit windows for vital signs.

Standing vital signs (SBP, DBP and pulse rate) will be summarized using mean, SD, minimum, maximum and median by treatment group and visit (Baseline, Day 1 2-hours post-dose, Week 8 / EOT). Additionally, a within-subject change will be calculated per visit as the post-baseline measurement minus the baseline measurement and summarized by treatment group and visit.

Table 23 describes PCS criteria for vital signs. The number and percentage of subjects with PCS values in vital signs using the subject's worst value during double-blind treatment period will be presented by each treatment group. The summary will include all vital signs at both scheduled and unscheduled visits. It will include resting and orthostatic (supine [average] and standing) vital signs. For criteria comparing with baseline, vital signs at standing will be compared with vital signs at standing and vital signs at supine (average)/resting will be compared with vital signs at supine (average)/resting.

Another summary will be created using the subject's worst value (resting vital signs only) during the follow-up period.

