- b) Height will be measured at screening only. Weight will be collected at screening, prior to randomization, week 4 and week 8/EOT.
- c) Any change between the screening and randomization visits will also be captured in the medical/surgical history.
- d) Continued subject eligibility to be confirmed based on laboratory results prior to having the subject wash-out of current pain medications (phone call). Continued subject eligibility to be confirmed based on completion of wash-out prior to having the subjects start baseline diary run-in (visit 2).

Footnotes continued on next page

- e) During screening period (wash-out): Study staff to contact the subject, if necessary, to initiate wash-out of current pain medications after continued eligibility has been confirmed. During follow up: Follow-up phone call 4 weeks (day 85) post study drug will be required.
- f) Subjects will be tested for drugs and alcohol at screening, baseline diary run-in and randomization. A positive test for tetrahydrocannabinol (THC) and/or opioids is allowed at the screening visit, but must be confirmed negative prior to baseline diary run-in and randomization.
- g) Continued subject eligibility to be assessed and confirmed based on daily average pain scores recorded in the e-diary prior to subject being randomized.
- h) Resting blood pressure and pulse rate values will be the average of the supine triplicates from the orthostatic measures for those days when orthostatic blood pressure is assessed. Pulse rate and blood pressure will be measured in triplicate after the subject has rested for at least 7 minutes in the supine position, each measurement approximately 1 minute apart (-3, -2, and -1 minutes before standing). Afterwards, the subject will be instructed to stand up within 10 seconds and remain free standing with no support on wall or furniture. Standing blood pressure and pulse rate will be measured after the subject has been in the free standing position at 3 minutes (every attempt should be made to take the measurement as close as possible to 3 minutes). Orthostatic vital signs will be captured on day 1 pre-dose and approximately 2 hours post dose and at week 8/EOT. Resting vital sign measurements should be collected at all other visits (except visit 2). All vital sign measurements should be conducted prior to blood draws. Body temperature will be assessed at screening, randomization and week 8/EOT only.

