### **5.4.1 Vital Signs**

Single measures of sitting resting blood pressure (SBP and DBP) and pulse rate values will be obtained at each visit (except for Visit 2) and should be conducted prior to blood draws. Blood pressure should always be measured on the same arm of the subject and preferably in the same position (sitting or supine).

Body temperature will be assessed at Screening, Randomization and Week 8/EOT only. The method of recording body temperature must be the same between visits (acceptable methods are oral or tympanic temperature).

Vital signs should be taken before scheduled blood draws.

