## 6.2 Safety Variables

The schedule of safety assessments is shown in Table 1. Baseline is defined as the last assessment on or prior to the first dose day (Day 1) of double-blind study drug.

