### **6.2.3 Vital Signs**

Vital signs variables are raw values (i.e., values at each scheduled visit) and changes from baseline in systolic blood pressure (SBP), diastolic blood pressure (DBP) and pulse rate at Day 1 2-hours post dose, Weeks 2, 4, Week 8/EOT and Week 10. Orthostatic SBP, DBP and pulse rate are assessed on Day 1 pre-dose, Day 1 2-hours post dose, Week 8/EOT (triplicate supine measurements approximately 1 minute apart [-3, -2, -1 minutes before standing] followed by a single standing measurement approximately 3 minutes after standing). Single resting measurements of SBP, DBP and pulse rate are measured on at Screening, Weeks 2, 4 and Week 10.

Orthostatic vital signs (SBP, DBP, pulse rate) will be derived for each subject as follows:

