**Table 13 Derivation of Orthostatic Vital Signs**

Analysis Time point	Item	Derivation
Baseline, Treatment period	Average supine result	Average of the non-missing supine triplicates taken approximately 1 minute apart (-3, -2, and -1 minutes before standing).
Day 1 2-hours post dose, Week 8/EOT	Orthostatic result	Standing result – Average supine result.  If the result for standing or average supine is not available, then the result will be set to missing.

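### SAP 7.5.4 pools supine triplicate averages with single resting readings, so vital-sign change from baseline at Weeks 2, 4 and 10 is not like with like

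*SAP*

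**What the plan says.** **Baseline.** SAP 7.5.4: "The baseline visit is the last measurement taken prior to the first dose of study drug". SAP 6.2 has a similar definition: "Baseline is defined as the last assessment on or prior to the first dose day (Day 1) of double-blind study drug". Either way the scheduled baseline is the Day 1 pre-dose value, not Screening.

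**Orthostatic days.** SAP 6.2.3: "Orthostatic SBP, DBP and pulse rate are assessed on Day 1 pre-dose, Day 1 2-hours post dose, Week 8/EOT". On those days footnote h to Protocol Table 1 says: "Resting blood pressure and pulse rate values will be the average of the supine triplicates from the orthostatic measures". SAP Table 13, which lists Baseline among its time points, derives the supine value as "Average of the non-missing supine triplicates taken approximately 1 minute apart".

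**Other visits.** SAP 6.2.3: "Single resting measurements of SBP, DBP and pulse rate are measured on at Screening, Weeks 2, 4 and Week 10". The SAP gives no posture for these readings, and neither does footnote h. Protocol 5.4.1 does: "Single measures of sitting resting blood pressure (SBP and DBP) and pulse rate values will be obtained at each visit (except for Visit 2". It adds that the same position, sitting or supine, is preferred from visit to visit.

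**Analysis.** SAP 7.5.4 summarises supine averages and resting values as one variable over Baseline, Day 1 2 hours post-dose, Weeks 2, 4, 8/EOT and 10, with change from baseline at each. For the Table 23 criteria that refer to baseline, standing values are compared only with standing values, but for the rest "vital signs at supine (average)/resting will be compared with vital signs at supine (average)/resting". Table 23 flags a rise or fall of at least 20 mmHg (systolic, diastolic) or 20 bpm (pulse) from baseline, using each subject's worst value in the treatment period. A separate follow-up summary uses resting values only.

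**The concern.** Change from baseline should reflect what happened after dosing. At Weeks 2, 4 and 10 it may also reflect a move from lying to sitting, and it certainly reflects a single reading set against a mean of three. At Day 1 2 hours post-dose and Week 8/EOT it reflects neither. The visit profile therefore alternates between comparable and non-comparable points. A movement at Weeks 2 and 4 that is gone by Week 8 could be an artefact read as a transient drug effect, or a real effect dismissed as an artefact.

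The SAP itself recognises that posture matters. It keeps standing values apart, and Table 24 sets outlier limits of 10 to 20 units for the step from supine to standing. It gives no reason for treating sitting and supine as interchangeable.

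Safety is one of the two primary objectives. Protocol 1.1 names slowing of the heart as a limitation of existing GABA-B agonists, so pulse and blood pressure are relevant to the mechanism under test.

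**Working it through.** The plan states no figure on this point, so there is nothing to reproduce. The check is a trace by visit, followed by two illustrations of size.

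**Trace** (SAP 6.2.3, 7.5.4 and Table 13; Protocol 5.4.1 and Table 1 footnote h)

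| Time point | Reading | Same kind as baseline? |
|---|---|---|
| Baseline, Day 1 pre-dose | Supine, mean of 3 | – |
| Day 1, 2 hours post-dose | Supine, mean of 3 | Yes |
| Week 2 | Single, resting (sitting per 5.4.1) | No |
| Week 4 | Single, resting (sitting per 5.4.1) | No |
| Week 8/EOT | Supine, mean of 3 | Yes |
| Week 10 (follow-up) | Single, resting (sitting per 5.4.1) | No |

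Two of the four scheduled time points in the treatment-period worst-value summary differ in kind from baseline. So does the only scheduled reading in the follow-up summary.

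**Illustration A: posture shift.** Let the change at one reading be normal with mean d (the shift) and SD s. The documents give neither value; d = 0 to +8 and s = 8 to 12 are assumptions.

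- P(rise ≥ 20) = 1 − Φ((20 − d)/s)
- P(fall ≥ 20) = Φ((−20 − d)/s)

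Example with s = 10 and d = 5: the rise is 1 − Φ(1.5) = 6.7% and the fall is Φ(−2.5) = 0.6%. With d = 0 each is 2.3%.

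| s | d = 0, rise / fall | d = 2 | d = 5 | d = 8 |
|---|---|---|---|---|
| 8 | 0.6% / 0.6% | 1.2% / 0.3% | 3.0% / 0.1% | 6.7% / 0.0% |
| 10 | 2.3% / 2.3% | 3.6% / 1.4% | 6.7% / 0.6% | 11.5% / 0.3% |
| 12 | 4.8% / 4.8% | 6.7% / 3.3% | 10.6% / 1.9% | 15.9% / 1.0% |

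A negative shift gives the mirror image. In an arm of 89 at one visit, with s = 10 and d = 5, expected flagged rises go from 89 × 0.0228 = 2.0 to 89 × 0.0668 = 5.9. Expected flagged falls go from 2.0 to 89 × 0.0062 = 0.6.

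**Illustration B: one reading against a mean of three, with no shift.** Let b be the between-visit SD and w the SD of a reading within a visit, both assumed, with independent readings.

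- Triplicate minus triplicate: variance 2b² + 2w²/3
- Single minus triplicate: variance 2b² + w² + w²/3

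Example with b = 6 and w = 6: the SDs are √(72 + 24) = 9.80 and √(72 + 48) = 10.95.

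| b | w | SD, both triplicate | SD, single vs triplicate | P(change ≥ 20 either way) |
|---|---|---|---|---|
| 6 | 4 | 9.09 | 9.66 | 2.8% → 3.8% |
| 6 | 6 | 9.80 | 10.95 | 4.1% → 6.8% |
| 6 | 8 | 10.71 | 12.54 | 6.2% → 11.1% |
| 8 | 4 | 11.78 | 12.22 | 8.9% → 10.2% |
| 8 | 6 | 12.33 | 13.27 | 10.5% → 13.2% |
| 8 | 8 | 13.06 | 14.61 | 12.6% → 17.1% |

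Both illustrations are for one reading. Table 23 counts each subject's worst value over scheduled and unscheduled readings, so neither estimates the percentage that will appear in the table.

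**The case against.** The strongest reply is that a posture mismatch is not established. Only Protocol 5.4.1 says sitting, and the same section prefers a constant position, so a site could properly take Weeks 2, 4 and 10 supine. The mismatch also arises from joining two passages that disagree. Read literally, 5.4.1 calls for a single sitting reading at Randomization and Week 8 as well, whereas footnote h calls for supine triplicates on those days. This stands. What is firm is an unreconciled instruction and a pooled analysis that allows a posture shift. The difference in number of readings does not depend on posture and is not met by this reply.

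Second, the damage is limited. Both arms follow one schedule, safety is compared descriptively with concurrent placebo, and no safety hypothesis is tested. The absolute limits in Table 23 (such as systolic below 90 or above 180 mmHg) do not use baseline, although posture can still move the reading itself. Two informative time points are matched: Day 1 2 hours post-dose, inside the 1.5 to 3 hour range for peak concentration, and Week 8, well past the roughly 9 days to steady state. Standing and orthostatic results are handled separately. All of this stands and limits the point to within-arm change and change-flag rates. It does not make the pooled series interpretable.

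Third, a reader might infer that the remedy is to use the single Screening reading as a matched baseline for Weeks 2, 4 and 10. The documents speak against it. Screening precedes wash-out of prohibited medicines, and Protocol 5.1.3 lists calcium channel blockers among these. Change from Screening could mix withdrawal of such medicines with the study-drug effect. It would also depart from the SAP's own baseline rule.

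**Conclusion.** The point holds in a limited form. As written, SAP 7.5.4 produces change from baseline and Table 23 change flags at Weeks 2, 4 and 10 that are not comparable with those at Day 1 2 hours post-dose and Week 8/EOT. Single-against-triplicate noise is present whatever the posture. A posture shift may be present, and it follows from the one passage that states a posture.

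Its size cannot be taken from the documents. Over the assumed ranges, a shift of +2 to +8 moves the per-reading rate of flagged rises from 2.3% to 3.6–11.5% at an SD of 10, and lowers flagged falls from 2.3% to 1.4–0.3%. Replicate noise alone raises flags in either direction from 2.8–12.6% to 3.8–17.1%.

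Two stronger readings should be resisted. One is that the comparison of ASP8062 with placebo is biased. The shared schedule gives no ground for that, although added noise and a common shift can obscure a real difference. The other is that the reported rates are known to be wrong by a given amount, which would require a posture and a shift that nobody has recorded in these documents. Week 10 is also a follow-up visit, so only Weeks 2 and 4 bear on the treatment period. The correction is worth making because it is cheap and safety is a primary objective.

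**What to change.** 1. Reconcile Protocol 5.4.1 with Table 1 footnote h and with the SAP's copy of that footnote, which leaves blood pressure out of its sentence on taking triplicates. State posture and number of readings once for each visit, so that they match the baseline.
2. In SAP 7.5.4, report change from baseline and the Table 23 change criteria separately for the supine-triplicate time points (Day 1 2 hours post-dose, Week 8/EOT) and the single-resting time points (Weeks 2, 4 and 10). Label the second set as differing from baseline in number of readings and possibly in posture. If item 1 makes all visits match, the split is needed only for readings already taken under the present wording.
3. Do not pool the two sets in the worst-value summary for the baseline-referenced criteria. The absolute limits can stay as they are.
4. Keep the Day 1 pre-dose baseline. Use change from Screening at most as a labelled supplementary summary, with the wash-out caveat stated.

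Items 2 to 4 need only SAP wording and programming on readings already scheduled. Item 1 needs a protocol clarification. The cost is a few more table rows and fewer time points in each worst-value summary.

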**Table 23 Potentially Clinically Significant Criteria for Vital Signs**

Vital Sign Parameter	Criteria	Worst Value
SBP	

• <90 mmHg

• Decrease of <math>\geq 20</math> mmHg from baseline

• <math>>180</math> mmHg

• Increase of <math>\geq 20</math> mmHg from baseline

	Lowest Lowest Highest Highest
DBP	

• <40 mmHg

• Decrease of <math>\geq 20</math> mmHg from baseline

• <math>>100</math> mmHg

• Increase of <math>\geq 20</math> mmHg from baseline

	Lowest Lowest Highest Highest
Pulse rate	

• <50 bpm

• Decrease of <math>\geq 20</math> bpm from baseline

• <50 bpm and decrease of <math>\geq 20</math> bpm from baseline (*)

• <math>>100</math> bpm

• Increase of <math>\geq 20</math> bpm from baseline

• <math>>100</math> bpm and increase of <math>\geq 20</math> bpm from baseline (*)

	Lowest Lowest Lowest Highest Highest Highest

(\*) Combination of values from the same time point.

Table 24 describes orthostatic outlier criteria for vital signs. The number and percentage of patients with orthostatic outlier values in vital signs will be presented by each treatment group at each post-baseline time point. For the overall during the double-blind treatment period, a subject's largest drop during that period will be used. The summary will also include results for the number and percentage of subjects where orthostatic challenge test lead to clinically significant results or symptoms.

**Table 24 Orthostatic Outlier Criteria for Vital Signs**

Analysis Time Point	Vital Sign Parameter	Criteria
Treatment period  Day 1 2-hours post-dose, Week 8 / EOT, Double-blind treatment period	Orthostatic SBP	≥ 20 mmHg decrease from average supine value
	Orthostatic DBP	≥10 mmHg decrease from average supine value
	Orthostatic Challenge Test	≥20 mmHg decrease from average supine value for orthostatic SBP OR ≥10 mmHg decrease from average supine value for orthostatic DBP
	Orthostatic Pulse rate	≥20 bpm increase from average supine value

### **7.5.5 Electrocardiograms**

The baseline visit is the last measurement taken prior to the first dose of study drug.

The number and percentage of subjects with normal, not clinically significant abnormal, and clinically significant abnormal results as assessed by investigator for the 12-lead ECG will be tabulated by treatment group at each treatment visit and time point (Baseline, Week 8, EOT and Week 10).

Number and percent of subjects with 12-lead ECG abnormalities as well as number and percent of subjects whose 12-lead ECG reading changed from normal at baseline to abnormal will be tabulated by treatment group at each treatment visit and time point (Baseline, Week 8, EOT and Week 10)

A shift table of the finding at baseline ('normal', 'abnormal - not clinically significant' and 'abnormal - clinically significant') to the worst finding during the double-blind treatment period and follow-up period will be presented by treatment group.

### **7.5.6 Physical Examination Findings**

Physical examination findings will be listed by treatment group.

### **7.5.7 Columbia Suicide Severity Rating Scale**

Number and percentage of subjects in each of the categories of C-SSRS described in Section 6.2.5 will be summarized at each analysis time point (Baseline, Week 2, Week 4, Week 8, EOT and Week 10) by treatment group. For each analysis time point, if a subject answers "yes" to more than one question within a category, the worst finding will be used.

For the overall during the double-blind treatment period and the overall during the follow-up period, a subject's worst finding during that period will be used.

All C-SSRS assessments will be listed only for subjects with at least one event of suicidality (suicidal ideation and/or suicidal behavior).

### **7.5.8 Pregnancies**

A detailed listing of all pregnancies will be provided.

## **7.6 Analysis of Pharmacokinetics**

PK assessments will only be performed in subjects treated with ASP8062. Summary tables of PK concentration will be provided for Day 1 (1-4 hours post-dose) and by sampling

timepoint (pre-dose, 1-4 hours post dose and >4 hours post dose) across Weeks 2, 4 and 8/EOT combined (see table below). Descriptive statistics will include n [number of samples], mean, standard deviation, minimum, median, maximum, coefficient of variation and geometric mean.

## PK Summary Table Schema

Week 1	Weeks 2, 4, 8/EOT		
1-4 hours post dose	Pre-dose	1-4 hours post dose	>4 hours post dose

A listing of sample times and concentrations will be provided.

